Nicotine replacement side effects (Aim II only): All subjects in Aim II who are tobacco users, ready to quit in 30 days, and cleared for use by the study team will be offered a free course of nicotine patches and/or the nicotine lozenge. Nicotine replacement treatment has been in clinical use for 20 years. It is available over the counter and has been judged to be generally safe and efficacious with very few contraindications. Nicotine replacement has been found to be medically safe for use with cardiac patients,¹²⁶ including specifically among ACS patients.^{127,128} Nicotine replacement is medically indicated for the vast majority of smokers with few exceptions (e.g., pregnancy). However, there are some reports indicating that nicotine replacement use poses risk to some subgroups of ACS patients in some situations¹²⁹. Thus, if nicotine replacement is provided, the dose will be determined in consultation with study team (i.e., [name]: psychologist/tobacco expert; [name]: cardiologist; [name]: family physician). The patient's primary provider will be informed through EPIC messaging that nicotine replacement was provided to the participant. The study MDs/PhD may talk to the patient to obtain more information in order to assess appropriateness of nicotine replacement. Initial dosing will follow FDA instructions/clinical guidelines, but lower doses may be provided if recommended by Drs. [name], [name], or [name]. Staff will be trained to explain the purpose of nicotine replacement, use, and side effects. Common side effects of the patch include local skin irritation at the site of the patch and disturbed or vivid dreams. Common side effects of the nicotine lozenge include mouth problems, indigestion, and sore throat. Less common reactions to both the patch and lozenge includes allergic reactions. If the dose of nicotine replacement is too large or if the participant continues to smoke at a high level while using the nicotine replacement, they may experience symptoms of nicotine overuse including nausea, irregular heartbeat or palpitation, and dizziness. The risk of using nicotine replacement in the current study is judged to be very minor.

Nicotine Withdrawal Symptoms After Quitting (Aim II only): There is a strong likelihood that most study HSR#17-4351 [05.17.17][10.05.17][07.26.18][09.09.19][10.22.19][11.04.19][01.28.20]

participants who quit smoking will experience some nicotine withdrawal symptoms, including anxiety, restlessness, anger, irritability, sadness, problems concentrating, appetite change and weight gain, insomnia, and decreased heart rate. Generally, these reactions are temporary and pose no serious health risks.

Injury from increasing physical activity (Aim II only): It is possible that physical activity post-ACS could trigger a recurrent cardiac event or cause other injury. The risk of injury from increasing physical activity in the current study is judged to be very minor, given that we will focus on increasing walking (rather than more intense exercise).

Confidentiality or loss of privacy. We will collect potentially sensitive information about participants; if released inappropriately, participants may experience embarrassment or distress. The seriousness of the consequences would depend on the nature of the information revealed and to whom the information was revealed. Given the numerous steps we take to protect participant confidentiality, we think the risk of a breach of confidentiality is low.

Discomfort or distress when completing assessment and treatment procedures. Some participants may feel uncomfortable or distressed answering personal or private questions during assessment or treatment. Some participants may also feel uncomfortable or distressed due to the collection of physical measures (e.g., weight). In our previous studies, when individuals did report discomfort in these situations, it was mild.

Worsening of depression and emergent suicidality. The post-ACS period can be a high stress time. Although not likely resulting from trial participation, it is likely that a minority of participants will experience worsening of depression or episodes of suicidality during this study.

2. Adequacy of Protection Against Risk

2a. Recruitment and Informed Consent

Participants who appear to meet inclusion/exclusion criteria, based on review of their electronic medical records, will be called by study staff. At first contact, all participants will first be given a brief verbal overview of the study. If participants agree to be screened and pass the screening questions based on inclusion/exclusion criteria they will be invited to participate. Written informed consent (including a description of the nature, purpose, risks, and benefits of the study) will be obtained from participants before initiating assessment. The voluntary nature of the study and the participant's right to withdrawal at any time will be stressed during the consent process; this information will be provided to participants in written form at the time of consent. As part of the consent process for Aim II, we will also ask five questions about the study. The staff member will clarify any misunderstandings that emerge during this process. Those who answer fewer than four questions correctly (after two tries) will be considered to lack the capacity to consent to the research. Research assistants and study interventionists will obtain consent.

2b. Protections Against Risk

Minimization of nicotine replacement side effects: Nicotine replacement is generally safe for patients with stable cardiac disease¹²⁶ and with post-ACS patients.^{132,133} However, there are some reports indicating that nicotine replacement use poses risk to some subgroups of ACS patients in some situations¹²⁹. **Thus, we will minimize the occurrence of any serious medical side effects by having the** study provider team (i.e., [name]: psychologist/tobacco expert; [name]: cardiologist; [name]: family physician) review if the patient is appropriate for nicotine replacement and if so what the dose should be. Initial dosing will follow FDA instructions and clinical guidelines, but lower doses may be provided if recommended by the study team. Participants will agree to consult with their outpatient medical providers regarding the safety of using nicotine replacement if their medical status changes after nicotine replacement is initially provided. Further, staff will be trained to explain the purpose of nicotine replacement, procedure for use, and side effects, as well as how to use nicotine replacement in a manner that minimizes risk.

To minimize skin reactions related to the nicotine patch, participants will be instructed to move the site of patch placement each day and to not repeat site use for at least one week. Smokers will be instructed to remove the patch before bed if it significantly interferes with sleep. To minimize lozenge side effects, participants will be instructed in proper use in detail (i.e., do not chew the lozenge).

Nicotine replacement dose may be adjusted downward if there is significant nausea or other reactions. Participants with severe side effects will be asked to discontinue nicotine replacement use and discuss with study team and/or their providers before continuing.

Only participants who are ready to quit within 30 days will be provided with nicotine replacement. Participants will be allowed to use the nicotine lozenge to reduce smoking in preparation for a quit day (i.e., consistent with a "cut down to quit" approach).

Minimization of nicotine withdrawal symptoms after quitting: Participants who decide to use the nicotine replacement will be told that it will reduce but not entirely eliminate withdrawal symptoms. Participants will be instructed to call their outpatient physician in the case of severe withdrawal reactions. Withdrawal symptoms typically abate within 1 to 2 weeks of quitting and are not medically dangerous.

Minimization of potential for injury from increasing physical activity: BA-HD focuses on increasing self-paced walking (i.e., goals well be stated in steps per day on wearable accelerometers/pedometers), which is safe for the vast majority of patients who are ≥ 3 months post-ACS. If the interventionist has any concern regarding the safety of walking [name] and [name] will be available for consultation. The patient may want to work on more intense exercise, especially later in the treatment protocol. If this is the case the interventionist will discuss with the patient if they have been cleared by their medical team to engage in the desired activity. If there is any concern regarding clearance for exercise, the interventionist may contact the patient's providers and/or consult with [name] and [name].

Minimization of loss of confidentiality/privacy: All data and records will be safeguarded according to the strict privacy/confidentiality policies of Hennepin Healthcare Research Institute's Institutional Review Board (IRB). Confidentiality will be maintained by numerically coding all data, disguising identifying information, and keeping data in secure electronic locations or locked in file drawers. All electronic data will be numerically coded and stored on a password protected computer in a secure research space. All paper forms will be stored in locked file cabinets in a locked room. Names of participants will be stored separately. Participant information will be accessible only to research staff, who are pledged to confidentiality and complete training in the ethical

conduct of research (i.e., both HIPAA and CITI trainings). [name] will also personally train staff on maintenance of participant confidentiality. Identifying information will not be reported in any publication.

Minimization of discomfort or distress when completing assessment and treatment procedures: We will take three specific steps to reduce the possibility of discomfort or distress:

Study will be clearly explained. A detailed explanation of the study, including what study participation would involve, the nature of the questions participants will be asked to answer, the nature of measurements, and the right to withdrawal from the study at any time without penalty, will be provided to the participants, both verbally and in writing (through the informed consent form). Participants will be encouraged to ask questions about the study. Individuals who are uncomfortable answering these types of questions, assessments, or interventions likely will not choose to participate. Those who choose to participate but are very uncomfortable with the questions, assessments or interventions will likely refuse these assessments or choose to withdrawal from the study.

Private setting. To help ensure clients' comfort, they will answer survey questions and complete physical measurements in a private setting. Thus, they should not be concerned that another individual would be able to observe these assessments.

Staff Training. All staff interacting with participants will be trained by [name] to ask questions and complete assessments in a sensitive manner and be supportive to any participant experiencing discomfort or distress.

Minimization of risk from worsening of depression and emergent suicidality. **There is no evidence indicating that participation in this trial will worsen depression or cause suicidality.** However, given that post-ACS period can be a high stress time, it is likely that a minority of participants will experience worsening of depression during this study. A smaller minority may experience episodes of suicidality. Thus, we will monitor and respond to these issues in an ethically sensitive manner.

For aim II, we are only enrolling participants who are not currently in counseling for depression. Participants taking an anti-depressant medication at baseline and during the study will be allowed to participate. For ethical reasons, once enrolled we will not restrict anti-depressant medication treatment seeking in any way during the study (i.e., we will not ask participants to refrain from starting antidepressant medication during the study). We will carefully track antidepressant medication seeking outside of the study and will control for outside treatment in analyses as appropriate.

All participants will be assessed for depression using the PHQ-9 at all assessments. If a participant continues to report significant depression (i.e., PHQ-9 ≥ 10) at the end-of-treatment assessment, staff will 1) encourage the participant to discuss these symptoms with his or her medical providers and 2) provide a list of community psychiatric treatment referrals.

If a participant reports active suicidality (i.e., any recent suicidal attempts, suicidal gestures, or self-injurious behavior; any current plan or intent to engage in suicidal or self-injurious behavior) to any study staff at any time point, the participant will be assessed by [name] (a licensed clinical psychologist). [name] will assess the participant and respond in an appropriate and ethical manner according to the standards of care for suicide prevention (e.g., referral to immediate emergency psychiatric care if danger to self is imminent).

3. Potential Benefits of the Proposed Research

Potential benefits for Aim II participants include free treatment with the potential to increase the likelihood of behavioral risk factor reduction, which could in turn extend their lives. Aim II participants will also receive free depression coaching, which can improve their quality of life. By participating in the research, all participants (both Aims I and II) will also benefit from knowing they may ultimately be helping others as they will have helped us develop and test an intervention. The costs of participating in the research will be minimized through our extensive efforts to maintain confidentiality, reduce discomfort or distress, and minimize medical complications. Overall, it is expected that the potential benefits to participants in the proposed study will outweigh potential risks.

4. Importance of the Knowledge to be Gained

The results of the proposed study will further our knowledge regarding 1) the relationship between behavioral risk factors and mood in post-ACS patients and 2) the utility of integrating Behavioral Activation based depression treatment with behavioral risk factor reduction for cardiac patients. This knowledge could lead to a reduction in post-ACS mortality rates. As discussed above, we expect that these benefits will outweigh potential risks to participants.

5. Data and Safety Monitoring Plan

We expect the proposed trial to be considered minimal risk by Hennepin Healthcare Research Institute's IRB. Given that the proposed Aim II research is a single site trial and our expectation of a minimal risk designation, the proposed trial does not meet NIH criteria requiring establishment of a formal Data and Safety Monitoring Board. However, we have a detailed data and safety monitoring plan for aim II to ensure the safety of all participants and the validity and integrity of the data. (Note: If our Institutional Review Board or the study sponsor unexpectedly decides that the proposed study includes more than minimal risk to participants, we will convene a Data and Safety Monitoring Board before recruitment begins.) The Data and Safety Monitoring plan is provided in a separate attachment.

6. ClinicalTrials.gov Requirements

The proposed clinical trial will be registered at www.clinicaltrials.gov.

Amendment 2: H³ Study Issued Cell Phone Protocol

If at time of recruitment or any time during treatment/follow-up study staff determine that the participant does not have access to or has lost access to regular phone access, the participant may be offered use of a H³ provided cell phone. Participants who are issued a study phone will complete the H³ Study Issued Cell Phone Agreement form. Patient will be instructed to return the H³ provided phone to staff upon completion of the 12w outcomes visit or at any time if it is determined that the participant no longer qualifies for the study or is not adhering to the guidelines outlined in the H³ Study Issued Cell Phone Agreement. Upon return of the device, participants will qualify for a \$20 stipend.

See Appendix A: Study Issued Cell Phone Agreement.

References

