Inclusion criteria: 1) ACS diagnosis (diagnosis of unstable angina, ST and non-ST elevation myocardial infarction) documented in medical record in the preceding 2-12 months, 2) Depression diagnosis listed on patient problem list in patient's medical record, a clinically administered PHQ-9 score of 10 or greater in the past 12 months indicated in the patient's medical record, or a Center for Epidemiologic Studies Depression scale (CESD) score ≥ 10 (indicating "likely major depressive disorder"); CESD will be administered by phone during screening if there is no indication of depression or PHQ-9 score within 12 months in the patient medical record, 3) current non-adherence to ≥ 1 of four behavioral risk factors (see below), 4) willing to make immediate changes to ≥ 1 relevant behavioral risk factors, 5) age of 18-75, 6) lives within 1.5 hours of Hennepin Healthcare, and 7) fluent in English.. Exclusion criteria: 1) Limited mental competency (as indicated in medical chart), 2) presence of current exacerbation of psychosis/serious mental illness or suicidality, 3) in hospice care, 4) currently attending regular counseling targeting depression or any health behavior change, and 5) currently attending a cardiac rehabilitation program (those excluded for being in rehabilitation will be re-contacted after completion). We will attempt to obtain a sample of at least 45% women, which is representative of the gender distribution of discharged ACS patients.¹

We will define non-adherence as follows: Tobacco non-adherence = use of any tobacco product in the last week. Physical activity non-adherence = engagement in < 90 minutes of moderate or greater physical activity per week.¹⁰⁴ Medication non-adherence = non-adherence based on Heart and Soul study criteria i.e., taking medication as prescribed 75% of the time or less, forgetting medications at least 1x/week, or skipping a medication at least 1x/week. Diet non-adherence = following a "healthful eating plan" 4 or fewer days per week, eating 5 or more servings of fruits and vegetables 4 or fewer days per week, or eating high fat foods 3 or more days per week.

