Behavioral risk factor change goals will be set alongside depression focused goals (see below) and the content of goals will be integrated to maximize both mood improvement and risk factor change. For example, for a participant trying to quit smoking, the interventionist will ensure that goals don't involve increased contact with smoking triggers. Likewise, the interventionist will encourage pleasant/valued activity content that is consistent with risk factor targets (e.g., walking, cooking healthy a meal with spouse) and discourage content inconsistent with risk factor goals (e.g., outings for ice cream).

Risk factors will be targeted sequentially. First, the interventionist and participant will collaboratively choose the first risk factor to target. This will primarily be based on what the participant is most motivated to change. If the participant is equally motivated to change two or more risk factors on which they are non-adherent, the priority order will be: 1) tobacco, 2) medication adherence, 3) physical activity, 4) diet. This priority order is based on strength of data implicating each as a mechanism of the depression to post-ACS mortality relationship.^{14-17,76-79} Next, the interventionist will provide brief education regarding the importance of that risk factor post-ACS, the recommended level of that risk factor for secondary prevention, and how their

current behavior compares to recommendations. This information will be based on the latest clinical guidelines.¹⁰⁹⁻¹¹¹ The interventionist will then collaboratively set an attainable goal regarding that risk factor until the next session and ask the participant to self-monitor engagement in the risk factor. A second and/or third risk factor could be targeted later in treatment if the participant makes sufficient progress on the first. The detailed content of coaching for each of the behavioral risk factors has been developed by the investigative team and is informed by clinical guidelines and our Aim 1 qualitative findings.

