
BA-HD will have the following structure: **Session 1** will be offered in our clinic or at home (based on participant need and preference). Session 1 will include the following: **1)** review patient history, **2)** review status of 4 health behavior targets, **3)** discussion of rationale for BA-HD, **4)** choice of initial behavioral risk factor target, **5)** brief education and history regarding chosen health behavior, **6)** introduction of self-monitoring of mood and behaviors (including relevant health behaviors), **7)** collaboration to set one activation goal to be completed before the next session, **8)** problem-solving of barriers to completion of goals, and **9)** offering an automated email or text message reminder of goals. Participants will be provided with a packet of educational materials to keep at session 1. If applicable, interventionist will engage providers and the study team (including study cardiologist) to assess for safety of physical activity or use of nicotine replacement.

Session 2 will be scheduled in person if possible. **Session 2** will include the following: **1)** follow-up on between session self-monitoring and any planned activities, **2)** a structured values assessment¹⁰⁷ and a HSR#17-4351 [05.17.17][10.05.17][07.26.18][09.09.19][10.22.19][11.04.19][01.28.20]

discussion of how resulting values relate to risk behaviors (e.g., “How will continued smoking detract from grandparenting?”), **3**) provision of tools to aid risk behavior change, **4**) collaboration to set 1-4 activation goals to work on before the next session, **5**) problem-solving of barriers to completion of goals, and **6**) offering an automated email or text message reminder of goals.

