Sessions 3-10 will be conducted by phone and will follow the same basic format: **1**) assess depressed mood, activity, and relevant behavioral risk factors between sessions, **2**) review adherence to activation goals from the previous session; **3**) choose 1-4 activation goals that are pleasant and/or in line with the participant’s values and explicitly schedule these; **4**) problem-solve barriers to completion of new goals, and **5**) offer an automated email or text message reminder of goals. Starting in session 4 the interventionist and participant will collaboratively discuss if the next relevant behavioral risk factor should be added to goals. During the final coaching call (session 10 if full protocol completed), rather than assigning new activation goals, the interventionist will guide the participant in completion of a written guide which provides a structure for continuing to work towards goals independently.

Measurement

Participants will complete self-report, interview, and anthropomorphic measures at enrollment and at end-of-treatment (i.e., following 12 weeks of BA-HD coaching). In addition, at end-of-treatment a 30-45 minute qualitative interview will be conducted. Participants will be compensated \$30 per assessment and an extra \$20 for completion of the qualitative interview. Thus, Aim II participants could receive \$80 total for assessments. Transportation will also be provided or reimbursed as well.

Variables assessed at baseline only: Socio-demographics, including age, gender, ethnicity, employment, and income will be collected. Medical history will be assessed through self-report and chart review and will include ACS diagnosis and treatment, and a detailed history of cardiac disease, events, and procedures. Co-Morbid conditions will also be assessed.

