Outcomes: Acceptability will be assessed only during the end-of-treatment assessment using the 8-item Client Satisfaction Questionnaire.⁹⁴ Feasibility will be assessed by rate of recruitment/retention, session attendance, and completion of between session goals. Depression symptoms will be assessed using the CESD and the 9-item self-report Patient Health Questionnaire (PHQ-9).⁹⁷ Composite Behavioral risk factor adherence: The Medical Outcomes Study Patient Adherence Questionnaire¹⁰⁶ has validated items measuring all four of the behavioral risk factors targeted (tobacco, physical activity, diet, medication adherence) and has been used in large studies of post-ACS risk factor change.¹¹³ Thus, we will use the total score of these items as a composite outcome across the 4 risk behaviors. We will calculate the total score for the 10 more general items related to cardiac health¹³⁵. We will also administer brief validated questions regarding time spent engaging in physical activity, medication adherence, and diet quality. Change in tobacco use will also be measured continuously with cigarettes/other tobacco product use per day and dichotomously using 7-day point prevalence abstinence (i.e., no use at all in past 7 days). A breath sample will be used to verify abstinence.^{117,118} Participants who report using smokeless tobacco products or e-cigarettes containing nicotine will be considered tobacco users. **Secondary outcomes:** We will also include established self-report measures of affect,¹¹⁹ health related quality of life¹²¹, exercise capacity,¹²² and hypothesized BA mediators.^{123,124} Weight/height, waist circumference, and resting systolic and diastolic blood pressure will be collected using standard procedures.

Analysis

Qualitative Data: We will again analyze recordings of end-of-treatment qualitative interviews using the Framework Matrix Analysis procedures described for Aim I above. However, analysis of follow-up interviews will explicitly focus on acceptability and suggestions for improving BA-HD.

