Consistent with successful BA manuals and our Aim 1 qualitative data, we plan to conduct a 10 session treatment over 12 weeks (weekly for the first 8 sessions and bi-weekly for the final two). The initial two sessions will be about 50 minutes long and later sessions will be 20-30 minutes long. We plan a treatment that is primarily over the phone, but allowing for the 1st and 2nd sessions in person and in home if needed per patient preferences. [name], a Hennepin Healthcare employed exercise physiologist, and/or an HHRI employed social worker will conduct all treatment in the proposed study.

1b. Sources of Materials

All data collection will follow IRB and HIPAA guidelines. Data will be collected directly from participants and from medical records. Data will include participant responses to interviews and self-report questionnaires (including screening questions), expired air samples (aim II for those focused on tobacco cessation only, i.e., carbon monoxide testing), physical measurements (aim II only, e.g., blood pressure, height, weight), and data pulled from medical charts. Coaching sessions (aim II only) and qualitative interviews (aim I only) will also be audio recorded (explicit permission to do so will be obtained).

As participants will be recruited via chart review (medical records will be screened in order to identify patients who may meet inclusion criteria), we will apply for a Protected Health Information (PHI) waiver from our IRB. All data will be treated as confidential and will never be stored or reported in association with identifying information. Participant responses to interviews and self-report questionnaires and information obtained from medical charts will be entered directly into a secure electronic database. Only the PI, Co-Is, and study staff that have completed training in the ethical conduct of research will obtain or have access to identifiable information. All data will be de-identified and filed according to participant ID numbers in secure storage. Any forms with identifying information (e.g., signed informed consent forms) will be stored separately. Only de-identified data will be published.

1c. Potential Risks

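### One Protocol section verifies 7-day tobacco abstinence by breath sample without restriction, another limits the samples to participants working on cessation; the two should be reconciled

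*Protocol*

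**What the plan says.** **Outcome.** The Outcomes paragraph of the Protocol's Measurement section scores tobacco use continuously and also "dichotomously using 7-day point prevalence abstinence (i.e., no use at all in past 7 days". It then states: "A breath sample will be used to verify abstinence". Neither sentence depends on which behaviour the participant worked on. The same paragraph adds: "Participants who report using smokeless tobacco products or e-cigarettes containing nicotine will be considered tobacco users".

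**Sampling.** Section 1b, Sources of Materials, in the human-subjects part of the Protocol, lists the data to be collected. For breath it gives "expired air samples (aim II for those focused on tobacco cessation only, i.e., carbon monoxide testing".

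**Who counts as a user at entry.** The Approach section gives: "Tobacco non-adherence = use of any tobacco product in the last week".

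**How a participant comes to work on tobacco.** In the BA-HD section, "the interventionist and participant will collaboratively choose the first risk factor to target", mainly according to what the participant most wants to change. The session 1 content includes "choice of initial behavioral risk factor target". For later sessions: "Starting in session 4 the interventionist and participant will collaboratively discuss if the next relevant behavioral risk factor should be added to goals".

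**SAP.** It does not mention tobacco, breath samples or verification. It plans descriptive analysis and effect sizes, with change from before to after treatment calculated in completers only.

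**The concern.** The outcome covers tobacco users whatever they worked on. The sampling rule in section 1b covers only those who worked on quitting. If staff follow section 1b, the same outcome is biochemically checked in some tobacco users and taken on trust in others.

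The split is not neutral. It is made after baseline and rests largely on motivation, which is plausibly related to quitting. Verified and unverified reports would then come from different kinds of participant, and any false report of quitting in the unverified group would raise the rate unchecked.

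Neither document says how an unverified report is scored or which denominator the abstinence rate uses. What is at stake is the credibility of one small descriptive rate, not a hypothesis test.

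**Working it through.** The plan states no figure for this outcome, and the sample size of 20 is given without a derivation, so there is nothing to reproduce. The check is a reading of the sections against one another, with simple arithmetic for scale.

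**Step 1. Do the two rules differ?** Measurement: breath sample to verify abstinence, no restriction by target. Section 1b: breath sample only for those working on tobacco. They give different answers for a tobacco user who did not target tobacco.

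**Step 2. Can such a participant exist?** Yes, on the Protocol's own rules.
- Entry requires willingness to change at least one relevant risk factor, which need not be tobacco.
- The first target follows motivation. Tobacco has priority only when motivation is equal across factors.
- A further target depends on sufficient progress with the first, and is discussed from session 4.

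A tobacco user can therefore complete treatment without ever targeting tobacco.

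**Step 3. Whose score is affected at week 12?** Classify baseline tobacco users by target and by report:

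| Targeted tobacco | Reports 7-day abstinence | Sample under section 1b | Verification needed |
|---|---|---|---|
| Yes | Yes | Yes | Yes |
| Yes | No | Yes | No |
| No | Yes | **No** | **Yes** |
| No | No | No | No |

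Only the third row is exposed. A person who reports continued use needs no verification.

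**Step 4. Does baseline matter?** The enrolment assessment comes before session 1, so the target is not yet known then. But no section calls for an enrolment breath sample, and someone defined as a user by recent use has no abstinence to verify. By week 12 the targets are known.

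**Step 5. Scale.** Inputs: 20 participants (Approach, Aim) and 31-37% cigarette smoking after ACS (Significance). The second is a background figure; applying it to this sample is an assumption.
- Expected users: 20 × 0.31 = 6.2 and 20 × 0.37 = 7.4, so about 6-7.
- Weight of one misclassified report: 1/7 = 14.3% and 1/6 = 16.7%, so about 14-17 percentage points.

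The documents do not give the share of tobacco users who would choose another target, so the number in the exposed row could lie anywhere from none to all of them.

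**The case against.** **The outcome definition already supports full verification.** The Measurement section is where the outcome is defined, and it has no restriction. Section 1b is a list of data sources, in a part of the Protocol that opens by saying its protections will be revisited once Aim II is designed. It also shows another sign of lagging behind: it mentions audio recording of qualitative interviews for Aim I only, while the Analysis section relies on recordings of the end-of-treatment interviews. A reader might infer from section 1b that abstinence is definitely unverified in users who did not target tobacco. The documents do not support that; they support a conflict between two current sections. This part of the objection stands.

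**The baseline timing has no consequence.** A reader might infer that the rule fails because nobody can know at enrolment whom to test. Step 4 shows that nothing depends on this. This also stands.

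**Selective reporting is not planned.** A reader might compare a rate among those tested with a rate among all users and call the difference bias. That comparison shows only a choice of denominator, and no section says the rate would be confined to those tested. What remains is that the denominator is unstated.

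**The size is a small-sample effect.** Any one person among 6-7 moves a rate by 14-17 points, whatever the verification rule. The real number of users may differ, because entry requires depression and at least one of four risk factors, and a completers-only analysis would lower it. The behavioural outcome singled out in the Analysis section is the four-behaviour composite, which does not use the breath sample. All this limits severity. It does not remove the contradiction.

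**Breath carbon monoxide does not fit every user.** The Protocol counts smokeless and nicotine e-cigarette users as tobacco users, but one of its own cited sources on cut-off levels (reference 118) presents breath carbon monoxide as a marker of cigarette smoking. Testing everyone would not verify those users. The objection is sound, and the fix has to allow for it.

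**Conclusion.** The point holds as an inconsistency of minor severity. The outcome definition and the data-source list disagree on who gives a breath sample. If the list is followed, reports of abstinence from tobacco users who worked only on other behaviours go unverified, along a split made after baseline and based mainly on motivation.

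The number affected is unknown and possibly zero. On the assumption that the 31-37% background prevalence carries over to 20 participants, a single misclassified report would shift the rate by about 14-17 points. The conclusion that the sections conflict does not depend on that assumption; only the size does. In a single-arm feasibility trial analysed descriptively, the consequence is confined to how far one small rate can be trusted.

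**What to change.** Change section 1b to match the Measurement section: at the end-of-treatment visit, every baseline tobacco user who reports 7-day abstinence gives a breath sample, whichever behaviour was targeted. No enrolment sample is needed.

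Add a scoring rule to the SAP:
- report abstinence with all baseline tobacco users as the denominator, and say so explicitly, because the SAP otherwise limits change to completers while the Protocol's Analysis section promises an intent-to-treat approach;
- count a smoker's unconfirmed report of abstinence as use;
- show self-reported abstinence separately for users of smokeless products or e-cigarettes.

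The SAP is dated 3/8/22 and is partly in the past tense, so data collection may be finished. In that case, apply the scoring and denominator rule to the data in hand and state how many reports of abstinence were verified.

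The cost is a sentence in the Protocol, a few lines in the SAP and, if collection is still open, a few more breath tests at a visit already planned. The reported rate may be less favourable.
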